- 1. reductions in weekly FI episodes (primary outcome) and,
- 2. improvements in validated incontinence scores, patient-centred FI-related symptoms and disease-specific and generic quality of life measures (secondary outcomes);

Design

[figure not shown]
The proposed study is a UK based multi-centre (at least 14 centres) double-blinded, placebo-controlled trial of 212 participants randomised to receive the intervention (PTNS) or sham (needle insertion and TENS): 106 in each arm. All participants follow an assessment period, recruitment, allocation, standard 3 month treatment protocol (one 30 min session per week) with primary outcome determined at 14 weeks on an intention to treat basis.

The following pragmatic considerations were included in study design:

- 1. All participants randomised who receive the first treatment will be included in the intention-to-treat analysis of primary endpoint. Those in whom post-treatment data are unavailable at 14 weeks for any reason (loss to follow up, failure to complete treatment) will have their outcomes defined using the interim bowel diary data collected between treatments 6 and 7 (Visits 7 and 8). Those who do not have this data available (again due to loss to follow up or failure to complete treatment) will be defined as non-responders and their 14 week outcome imputed from their baseline FI frequency. Prior to the first treatment, it is anticipated that some participants (up to 10%) will fail to attend after eligibility is assessed due to a failure of compliance with the travel and attendance needs of the treatment course or study. These will not count as study recruits. Based on our own department's data and supported by the study of Peters et al., [41] it is anticipated that the dropout rate after the first intervention is complete will be 6%. This level is acceptable to analyse secondary endpoints using available case analysis. The reason for this interim bowel diary assessment is two-fold;
 - a. to gauge response to a short course of treatment (since some people believe a 12 week course is not necessary);
 - to allow us to collect 'real' data regarding those participants who do not complete the full 12 week course of treatment, in an attempt to judge whether this was due to objective lack of response.

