
These will be assessed using bowel diaries and investigator-administered questionnaires. Bowel diary data will be collected at week -2 to 0 where 0 is start of treatment and -2 is baseline pre-randomisation, and at 14 weeks for the 2 preceding weeks post intervention i.e. weeks 12-14. There will also be a 1 week bowel diary collected between Visits 7 and 8, half way through the treatment duration. This is when participants usually start to perceive benefit. This will help to improve the quality of data on participants who withdraw from the study as outcomes will be analysed using the last available data on those participants who do not complete the final 2 week bowel diary. In those patients who withdraw from the study prior to completing the final study visit no secondary outcome data will be available for analysis. The bowel diaries will record number and type of incontinence episodes per week (and associated symptoms). An episode of faecal incontinence is defined as 'any episode considered significant enough by the participant to include on their bowel diary'.

Primary:

Responder vs. non-responder: Defined as a 50% or greater reduction in FI episodes per week (on intention-to-treat).

Secondary:

- a. Percentage reduction in FI episodes per week in addition to informing the primary outcome, this will give a confidence interval of effect and permit calculation of the proportions of patients who achieve complete continence or no change / deterioration (used in one Cochrane review of surgery for FI: [53]).
- b. Mean reduction in FI episodes per week. The confidence interval of this measure will be important for clinical interpretation of effect.
- c. Validated and reliable patient-rated quantitative outcomes including symptom severity scores (Cleveland Clinic Score) [50], validated disease-specific: FI-QOL [24] and generic: EQ-5D [54] quality of life measures will be employed.

- d. Recently-described patient-centred qualitative outcome tools have identified 5 key issues [8]. These will be employed as suggested by NICE (2007) research recommendations [32] and are anticipated to provide more clinically meaningful outcomes.
- e. Likert scales of patients global impression of success (0-10). These have been employed infrequently in the FI literature but will help to validate the primary outcome (a).
- f. Short urinary symptom assessment. As many patients have combined FI and urinary incontinence symptoms it will be of value to assess both.

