The SAE will be recorded in the participants' CRF folder and the participant followed up with regular phone calls and at the following appointment the following week. The SAE form is scanned and emailed or faxed to the sponsor. The email address the form should be sent to at the Joint R&D Office (JRO) is: [contact]

The fax number is: [name]

There are no SAEs expected to occur in this population. Therefore, all related SAE's are reportable as outlined above.

Withdrawal Criteria

Participants will be withdrawn from the trial if they fulfil any of the criteria below at any point following delivery of the first treatment.

- Participant no-longer wishes to be involved in trial
- Participant develops medical condition which fulfils part of the exclusion criteria
- Participant becomes pregnant
- If, for any reason, the participant has to be unblinded
- Participant lost to follow up (could not be contacted by telephone or other means)
- Intercurrent illness
- Death

When a participant is withdrawn from the study, the Early Withdrawal from Study CRF will be filled in by a researcher. In order to ensure clarity of each participants outcome, the researcher should also complete the final study visit (CRF 7).

Once a participant has withdrawn from the trial, they will be followed up on the NHS in the usual way, and progress down the usual treatment protocol.

Proposed sample size

Previous publications [36-39] and our own data [40] on 50 patients suggest a 60% success rate for PTNS on the basis of above justified primary outcome measure. There are no RCT data for PTNS in FI. However the pivotal level I SumiT trial of PTNS in overactive bladder symptoms (OAB) [41] which used a similar global response assessment of urinary incontinence and intention to treat design, observed a moderate or marked improvement in symptoms in 55% PTNS group and only 21% sham group. On the basis that placebo responses are frequently higher for bowel rather than bladder symptoms [43-45] we have selected a sham response rate of 35% whilst keeping this more conservative estimate of treatment response of 55%. We believe this difference remains clinically important in relation to other therapies such as SNS. 212 participants are required to detect this difference with 80% power at the 5%

significance level. We will recruit 235 participants at baseline to allow for a 10% failure to attend the 2nd visit (allocation and first intervention).

Feasibility

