Outcomes will take the form of binary (success or failure: primary outcome measure), count (change in number of FI episodes), ordinal (patient's global impression of success) and continuous (GIQOL, SF36, FI score, and EQ-5D) data. Regression models, with a fixed effect for centre, appropriate to the outcome data types will be fitted to estimate the treatment effect, adjusting for baseline values (when appropriate), sex, and loperamide use/fibre supplements as potential confounders (the dose and frequency of these will be recorded at all visits). Analysis will be performed using proprietary software (Stata version 10.1, Stata Corp. Texas) by the PCTU study statistician ([name]). P < 0.05 will be taken to indicate statistical significance. Given the stability of FI over a short period of time, where follow-up scores are missing, these will be imputed using the baseline scores, or interim bowel diary scores if available. The rationale for this is that primary outcome would, in the absence of any intervention, be expected to remain stable over the relatively short time span of the trial. Any changes or deviations from the original statistical plan will be described and justified in the Clinical Study report. Every attempt will be made to avoid any deviations from the original statistical plan.

Ethical approval

PTNS is CE-marked and clinically established in the NHS. A favourable ethical opinion has been given (ELCHA REC 10/H0703/25 June 2010); Amendment 1 approved 19th Oct 2010 and Amendment 2 approved 6th June 2011.

PTNS treatment and placebo have no recognised significant adverse effects. Although the trial necessarily delays 'real' treatment of participants in the sham arm, this time has been limited to just over 3 months (discussed with [name], Prof of Bioethics and Law, QMUL). PTNS or an alternative treatment e.g. SNS can be offered immediately thereafter. We believe that the importance of the research question with subsequent major implications to NHS service delivery merits this modest delay. The trial will not affect prompt delivery of PTNS or other NHS treatments to non-trial patients.

Early Termination of Study

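### Withdrawal from the trial ends week-14 data collection for events that do not prevent it, and the set labelled intention-to-treat leaves out anyone randomised but untreated

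*Protocol*

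**What the plan says.** The Withdrawal Criteria section opens: "Participants will be withdrawn from the trial if they fulfil any of the criteria below at any point following delivery of the first treatment". Some of the listed reasons remove the participant from reach or remove consent: no longer wishing to take part, loss of contact, death. Others do not: having to be unblinded for whatever reason, intercurrent illness, pregnancy, or a new condition that meets an exclusion criterion. The section continues: "Once a participant has withdrawn from the trial, they will be followed up on the NHS in the usual way". An early-withdrawal form and CRF 7 are completed, but CRF 7 is a form for the principal investigator. The outcomes come mainly from the bowel diary and the CRF 3 questionnaires.

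Under Trial outcomes (Clinical outcomes) the protocol adds: "In those patients who withdraw from the study prior to completing the final study visit no secondary outcome data will be available for analysis".

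Design, pragmatic consideration 1, sets the analysis population: "All participants randomised who receive the first treatment will be included in the intention-to-treat analysis of primary endpoint". It names not completing the treatment course, beside loss to follow-up, as a reason why week-14 data may be unavailable. It then substitutes the interim diary kept between Visits 7 and 8 or, if there is none, a non-responder score with the baseline frequency. It accepts an available-case analysis for secondary endpoints. The Plan of Statistical Analysis says instead that missing follow-up scores are imputed from baseline, or from the interim diary where there is one.

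Under Events at each visit, the researcher randomises at Visit 2, is unblinded by doing so, and then gives the first treatment at the same visit.

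**The concern.** Leaving treatment and leaving follow-up are different things, and the withdrawal rule joins them. A participant who becomes pregnant, falls ill or is unblinded can usually still keep a two-week diary and fill in a questionnaire, but the plan stops asking. It thereby creates missing outcomes and then fills them by single imputation or leaves them empty. The reasons for leaving may be related to response or to arm, so these are not safely ignorable losses. The loss also carries into the one-year addendum, which takes only participants who completed the trial.

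The second limb is the label. A set that requires a first treatment is a modified intention-to-treat set. The condition is applied after the person giving that treatment has seen the allocation, so an exclusion could in principle depend on arm.

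An analysis plan cannot repair the first limb: it cannot recover a diary that was never requested.

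**Working it through.** **Inputs, all from the protocol**
- Response rates (Proposed sample size): "we have selected a sham response rate of 35% whilst keeping this more conservative estimate of treatment response of 55" per cent, so p1 = 0.55 and p2 = 0.35.
- Size (Design): "106 in each arm", 212 in total, for 80% power.
- Significance (Plan of Statistical Analysis): "P < 0.05 will be taken to indicate statistical significance". Sidedness is not stated; two-sided is assumed, because it is the only variant tried that reproduces 212.
- Dropout after the first treatment (Design, consideration 1): 6%. No rates by arm are given.

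**1. Reproducing the plan's figure.** For two proportions with mean p = 0.45:

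n = [1.96·√(2·0.45·0.55) + 0.842·√(0.55·0.45 + 0.35·0.65)]² / 0.20² ≈ 95.9, so 96 per arm.

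With the continuity correction, n′ = (n/4)·[1 + √(1 + 4/(n·0.20))]² ≈ 105.7, so 106 per arm and 212 in total. This matches. The recruitment figure of 235 follows from 212/0.90 = 235.6. That allowance covers people lost before allocation; it does not cover the 6%.

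**2. How many people.** 0.06 × 212 = 12.7, about 13. Only some are recoverable, since the 6% includes refusals and lost contact. The one indication is in Preliminary data: 3 of 53 patients started but did not finish, two because of pregnancy (a listed trigger that still allows a diary) and one through dissatisfaction. Three people are too few to project from.

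**3. Labelled worst case for power.** Assume 6% withdraw in each arm, would have responded at the planned rates, and are all scored as non-responders (nobody has an interim diary):
- PTNS 0.55 × 0.94 = 51.7%; sham 0.35 × 0.94 = 32.9%; difference 18.8 points instead of 20.
- Power on the continuity-corrected basis is Φ{[(d − 1/106) − 1.96·√(2p(1−p)/106)] / √[(p1(1−p1) + p2(1−p2))/106]}, with p the mean of the two rates.
- Full follow-up: (0.1906 − 0.1339)/0.0669 = 0.846, giving 80.1%.
- 6% scored as non-responders: (0.1786 − 0.1330)/0.0666 = 0.684, giving 75.3%.
- Without the correction the same step is 83.8% to 79.6%.
- Other assumed withdrawal rates (corrected basis): 3% gives 77.8%, 10% gives 71.9%, 20% gives 62.9%.

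**4. Bias between arms.** With equal withdrawal and no true effect, type I error stays at 5%. Bias needs unequal withdrawal, which has to be assumed. With 35% response in both arms and withdrawals scored as non-responders (uncorrected test):
- 2% PTNS v 10% sham: 0.35 × 0.98 − 0.35 × 0.90 = 2.8 points, type I error about 7.2%.
- 0% v 12%: 0.35 − 0.35 × 0.88 = 4.2 points, type I error about 10%.

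**5. The sections side by side.** On secondary outcomes after withdrawal, Clinical outcomes says none will exist, Design says available case, and the Plan of Statistical Analysis says missing scores are imputed. These cannot all apply.

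**The case against.** Several stronger readings are tempting and the documents do not support them.

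- *Withdrawn participants are dropped from the primary analysis.* They are not. Design, consideration 1, keeps every treated participant, through the interim diary or as a non-responder. The withdrawal rule therefore does not itself break intention-to-treat; it produces avoidable missing data.
- *Stopping treatment is a withdrawal criterion.* It is not on the list. The link comes only from Design, which names an incomplete course as a reason why week-14 data may be unavailable. It does not say that the diary is refused to such people, and Events at each visit tells sites to try again for missed interim and final diaries. What is missing is a positive instruction to seek the week-14 diary after treatment stops.
- *Many randomised people are excluded.* Randomisation and first treatment share Visit 2, and the 10% who fail to attend are lost before allocation.
- *The result will be biased.* No differential withdrawal is documented. The protocol expects almost no adverse effects, and under Breaking Randomisation Code it finds a need to unblind hard to imagine.

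Two further points are fair. The interim diary gives observed, not invented, data for people who leave after Visit 8, so scoring everyone as a non-responder is an extreme. And a week-14 diary completed after unblinding, or after the participant has moved on to other therapy, is not clean: an episode is whatever the participant thinks worth recording. Using it also answers a slightly different question from scoring the person as a failure.

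These points limit the size. They do not explain why an obtainable outcome should go unrequested, and one mid-course week is a weak substitute for two weeks after the end of treatment.

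**Conclusion.** The point holds in a limited form. As written, the protocol ends week-14 data collection for unblinding, intercurrent illness, pregnancy or a new exclusion condition, and plans for week-14 data to be unavailable when treatment is not completed. The primary outcome is then substituted and the secondary outcomes are absent or imputed, depending on which section is followed. The population called intention-to-treat is a modified one, though the people it omits should be very few.

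About 13 of 212 are affected in all, and fewer could be recovered. The worst case is a loss of 1.2 points in the difference (20 to 18.8) and about 5 points of power (80.1% to 75.3%). It rests on 6% in each arm, response among leavers as planned, no interim diaries, and the two-sided continuity-corrected test that reproduces 212. Any bias between arms depends on assumed, undocumented differences in withdrawal. The sample size calculation itself is sound. The change is worth making because it is cheap and has to be made while data are still being collected.

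**What to change.** - Leave the reasons for stopping treatment as they are. Add that stopping treatment, illness or unblinding does not end follow-up.
- Seek the two-week diary and CRF 3 at week 14 from everyone except those who withdraw consent for data, cannot be contacted or die. Use post, email or telephone where needed; the addendum already uses these routes.
- Define the primary analysis set as all randomised participants, by allocation.
- Reconcile Design (consideration 1), Clinical outcomes, Withdrawal Criteria and the Plan of Statistical Analysis, so that one rule governs missing primary outcomes and one governs missing secondary outcomes.
- Flag diaries completed after unblinding or after other therapy, and examine their influence in a sensitivity analysis.

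The cost is protocol wording and modest site effort for about 13 participants at the planned dropout rate. The price in interpretation is that some recovered diaries will reflect knowledge of allocation or other treatment, which the flag and the sensitivity analysis are there to show.

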- 2. We have elected not to implement 'ideal' trial conditions by dictating the cessation of all other medications during the RCT (with prescribed breakthrough medication protocols). It was felt that compliance would be low with such an instruction and that the effect size could be thus reduced by undocumented greater use in the sham arm. It was deemed preferable instead to permit ad libitum use of medications e.g. loperamide or fibre supplements but record this at each appointment as a potential confounder which could be subsequently included as a covariate in the analysis. In any case, the majority of participants have already failed using simple medications so regular usage is expected to be low.
- 3. It is accepted that the sham stimulation could be described as an 'alternative treatment' rather than a placebo. Although sham effects may result from both 'true' placebo responses [42,44], acupuncture [47] or 'electro-acupuncture' [51], the aim of this study is to determine the specific (perhaps additive)

effects of episodic low frequency electrical stimulation of the posterior tibial nerve as per the manufacturer's protocol.

Figure 1: trial protocol

Study centre eligibility

Participating centres have been selected from specialist clinics with nurse-led incontinence services. Only those centres with experience of PTNS will be eligible to participate. The applicants have already had interest from over 20 centres. However only those who at the time of the study commencement have received both specialist training under the guidance of the manufacturer and lead specialist nurse, and who have completed a minimum of 3 complete participant treatments i.e. 36 individual 30 minute treatments will be deemed eligible. Each centre will require a minimum of 2 staff with GCP training: one to perform baseline assessments, consent, allocation and intervention, and one to perform outcome assessments. Each centre is also required to input a minimum of 5 participants into the trial.

Participant recruitment

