Visit 3-13: intervention – interim information: At appointments 3-13, a member of the local team (which may be the same member as in Visit 2) will deliver the 30 minute intervention. They will check on CRF 4, prior to commencement, to make sure of the randomisation allocation, either PTNS or sham.

During this appointment with the participant, the researcher will enquire about adverse events, concomitant medication usage and pad usage, and record these on CRF 5.

At Visit 7, participants will be given a one week interim bowel diary to fill in between Visits 7 and 8. This bowel diary will then be collected and checked at Visit 8. Intervention parameters will also be entered on CRF 5.

At Visit 13, participants will also be given a two week bowel diary and CRF 3 questionnaire document to complete prior to attending Visit 14, two weeks later.

Visit 14: final study visit: The final study visit will be performed by a blinded member of the research team (i.e. somebody who has not been present at visits 2-13).

At this appointment, the bowel diary and CRF 3 questionnaire document will be collected and checked for completeness. The participant will then be asked to complete CRF 6, the post treatment questionnaire.

The research member will then ensure all documents are present and filled in correctly, and then ask the PI to complete and sign CRF 7. Once this has all been completed, the participant can be unblinded as to their treatment allocation if they wish. This is the final study visit, so further follow up should be arranged at this visit.

If participants have failed to complete the Interim Bowel Diary between Visits 7 and 8, this should be attempted again the following week. This is a Protocol Deviation, and therefore a 'Note to File CRF' should be completed to explain this. If participants fail to complete the Final Bowel Diary, again this should be attempted again after Visit 14, and participants brought back to collect this. This is also a Protocol Deviation, and should be documented in a 'Note to File CRF'.

After completion of trial: After Visit 14, participants who received 'sham' stimulation will be offered PTNS at this time, if they wish.

Participants who received real PTNS who derived significant benefit, will be offered 'top-up' sessions on an ad hoc basis, and will be followed up in NHS clinics in the usual way.

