Sham arm: the same protocol is followed as above. The only difference is that the needle will be inserted only 2mm into the skin and subcutaneous tissue i.e. just in far enough to not fall out and not deep enough to be close to the posterior tibial nerve. The lead will then be taped to the participants leg near to, but not touching the needle. The purpose of this is to prevent unbinding in the event of the participant inadvertently seeing the equipment. The PTNS surface electrode (A) on the calcaneous is also attached as above. The two active TENS surface electrodes (B & C) are employed as demonstrated below, with one under the little toe and one on top of the foot. Once all equipment is set up, the practitioner picks up both the Urgent PC machine and the TENS machine, one in each hand. Both machines are turned on. The TENS machine should be set to a pulse frequency of 10Hz and a pulse width of 200 microseconds. Then, pressing buttons simultaneously on the Urgent PC and the TENS machine, the practitioner should increase the adjustable current setting (which ranges from 0-10mA in preset 1mA increments on the TENS machine) and in the usual way determine the setting for therapy by observing the participant's sensory or foot for toe / ankle extensor motor responses, the current is reduced by one level for therapy. The reason both machines are picked up together is so that the audible sounds produced by the Urgent PC stimulator are the same in both the PTNS and sham arms, to decrease auditory variation between the study arms.

Figure 3: PTNS needle and surface electrode (A). TENS surface electrode placements (B & C). Note: The PTNS and TENS electrodes are inserted / connected on all subjects identically.

Randomisation

Participants will be randomised, with allocation concealment, at visit 2 using a web-based computer program to receive either PTNS or sham. This will be performed using a bespoke programme designed and held at the Nottingham Clinical Trials Unit. Study centres will input the unique participant identifier and gender of the participant and immediate on-screen randomisation will occur. This information should immediately be recorded on CRF 4 (randomisation information), which is stored separately from the other CRFs.

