Stratification will occur in the following way; strata 1 = men; then women will be stratified by centre. Stratification by gender will be used to reduce the potential confounding effects of variation in outcomes between male and female participants. Males represent approximately 10% of patients and have differing pelvic physiology and often disease aetiology (e.g. post anal surgery rather than childbirth). As only 1 or 2 male participants are expected to be enrolled from each centre, randomisation stratified on centre would allow the possibility that all the males are allocated to PTNS by chance. To avoid this scenario, we will therefore only stratify women by centre, so achieving near balance of PTNS and sham arms and ensuring comparability by centre.

Allocation concealment

Blinding of participants: For both interventions: (1) a standardised description of the techniques will be read from a card (See Appendix 2). This will describe an electrical sensation variably in the ankle or foot with or without motor responses in the foot (note: there is significant variability in conscious sensation and motor responses even between participants undergoing only PTNS); (2) the lower extremity will be draped from view; and (3) the audible sounds produced by the Urgent PC unit will be identical.

Performance bias considerations: Since the sham group might be expected to seek more advice than the treatment arm (if the hypothesis that PTNS is more effective than placebo is correct), the interaction of the administering nurse / physician will be standardised so that general supportive advice given at consultations is identical for all participants. This will be limited to a general welcome, answers to any concerns (whilst recording adverse events), advice on loperamide dosages and pad use (both recorded in outcome variables).

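### The treatment-effect models adjust for loperamide and fibre use without limiting it to use before randomisation, so the estimate can move away from the intention-to-treat effect

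*Protocol*

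**What the plan says.** The Plan of Statistical Analysis describes regression models, with centre as a fixed effect, "appropriate to the outcome data types will be fitted to estimate the treatment effect, adjusting for baseline values (when appropriate"), and then "sex, and loperamide use/fibre supplements as potential confounders (the dose and frequency of these will be recorded at all visits"). The outcomes listed just before include the binary primary outcome, and the Protocol gives no other model for it. The word baseline is attached to the outcome values and not to the medication.

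Pragmatic consideration 2 under Design explains why the medication is of interest. The trial will "permit ad libitum use of medications e.g. loperamide or fibre supplements" and will "record this at each appointment as a potential confounder which could be subsequently included as a covariate in the analysis". The same paragraph expects regular use to be low. Item i under Other recorded variables (Trial outcomes) repeats that drugs and dosage are noted at each appointment because they might turn out to be confounders.

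On timing, the Randomisation section says: "Participants will be randomised, with allocation concealment, at visit 2". At Visits 3 to 13, "the researcher will enquire about adverse events, concomitant medication usage and pad usage, and record these on CRF 5". CRF 5 is also completed at Visit 2, but by then the participant has been randomised and has had the first session. Table 2 lists a concomitant medications log at Visit 2 without placing it before or after allocation.

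**The concern.** A confounder must precede treatment and be associated with it for reasons other than treatment. Randomisation removes such associations in expectation, so use before allocation needs no correction for bias, although adjusting for it may add precision. Use after allocation is different. It may lie on the path from treatment to outcome, for example when a participant who feels better takes less loperamide. It may also reflect how badly the participant is doing. Adjusting for a mediator removes part of the treatment effect or adds to it. Adjusting for a marker of severity that also depends on arm makes participants with the same recorded use unlike each other across arms.

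The Design section declares an intention-to-treat comparison for the primary endpoint. A model that conditions on use during treatment answers another question, and the Protocol does not say that this is intended. At stake is the trial's main effect estimate, which is meant to inform national policy on PTNS.

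**Working it through.** **1. The plan's own figure.** Inputs from Proposed sample size: response 55% v 35%, 80% power, 5% significance (two-sided assumed).

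Uncorrected n per arm = [1.96 × √(2 × 0.45 × 0.55) + 0.8416 × √(0.55 × 0.45 + 0.35 × 0.65)]² / 0.20² = (1.379 + 0.580)² / 0.04 = 95.9, so 96.

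With continuity correction: (95.9 / 4) × [1 + √(1 + 4 / (95.9 × 0.20))]² = 105.7, so 106 per arm and 212 in all. This reproduces the plan.

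The target effect is a risk difference of 0.20, or an odds ratio of (0.55/0.45) / (0.35/0.65) = 2.27. Without the correction, power at 106 per arm is 84%.

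**2. Use as a marker of severity only.** The Protocol gives no usage rates and no link between use and outcome, so everything here is assumed. Let T be arm, S an unmeasured severity drawn from N(0,1), L any on-trial use and Y response:

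- logit P(L) = −0.8 − 1.0T + 1.0S, giving use of about 18% on PTNS and 34% on sham
- logit P(Y) = −0.75 + bT − 1.0S, with b = 1.0 giving about 55% v 35%, and b = 0 for no PTNS effect

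Odds ratios come from 1,000,000 simulated participants and rejection rates from several thousand trials of 212.

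| Assumption | Odds ratio, without L → with L | Rejection rate, without L → with L |
|---|---|---|
| 18% v 34%, PTNS works | 2.28 → 2.08 | 84% → 74% |
| 18% v 34%, no PTNS effect | 1.00 → 0.89 | about 5% → about 7% |
| As above, both severity coefficients 1.5 | 1.00 → 0.84 | about 5% → about 9% |
| About 11% v 14%, PTNS works | 2.26 → 2.23 | 84% → 83% |

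In repeated runs the third figure of interest, the 7%, varied between about 6% and 7%. In both null rows the adjusted odds ratio is below 1, so the excess rejections favour sham.

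**3. Use that itself improves response.** Here the total effect is held at 55% v 35% (risk difference 0.20) and L raises the odds of response. The risk difference is the cleaner scale: adding any prognostic covariate moves a logistic odds ratio slightly even without bias.

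| Use, sham v PTNS | Effect of L on response | Adjusted odds ratio | Adjusted risk difference |
|---|---|---|---|
| 10% v 10% | OR about 2.7 (log odds 1.0) | 2.31 | 0.200 |
| 15% v 10% | OR 2 | 2.38 | 0.209 |
| 30% v 15% | OR 2 to 3 | 2.57 to 2.78 | 0.225 to 0.236 |
| 50% v 25% | OR 3 | 3.21 | 0.263 |

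With equal use in the arms there is no bias. With unequal use the estimate moves towards PTNS. If the total effect is null (35% in both arms), the adjusted odds ratio is 1.12 at 30% v 15% with OR 2, and 1.33 at 50% v 25% with OR 3.

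**4. Reading the results together.** The same covariate can shrink or inflate the effect, depending on a mechanism that the trial does not measure. The adjusted result therefore cannot be called conservative in advance.

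**The case against.** The strongest reply is that the covariate is not pinned down. The parenthesis says only when use is recorded, those visits include Visit 2, and Design says that use could be included. The choice of measurement might be left to a statistical analysis plan that is not at hand, and a pre-randomisation covariate would do no harm. This stands in part: a harmless reading exists. But the analysis section states the adjustment as planned, calls the variable a confounder and ties it to all visits. Design and Trial outcomes both give ad libitum use during treatment as the reason for recording it. The text leans towards on-trial use, and nothing excludes it.

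The second reply is that use may be low. This stands. Design expects so, and at about 11% v 14% the change is negligible.

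A reader might infer more than the documents support:

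- **That the Protocol predicts heavier use on sham.** The remark that "the effect size could be thus reduced by undocumented greater use in the sham arm" concerns the design that was rejected, in which other medication would have been stopped. It shows awareness of the mechanism and is not a forecast for the chosen design.
- **That unblinded staff will drive use apart.** Allocation concealment does list "advice on loperamide dosages and pad use (both recorded in outcome variables") among staff interactions. It also makes that advice the same for all participants, who are blinded.
- **That adjustment always costs power or risks a false claim for PTNS.** Section 3 of the working shows power is not always lost. In the severity-marker scenario the false rejections run against PTNS. That null scenario also requires blinded allocation to change use with no effect on response, which is a strained combination.

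**Conclusion.** The point holds as a defect in the stated analysis rule. The Protocol admits post-randomisation medication use into the only primary model it gives, on the mistaken ground that such use can confound a randomised comparison. Bias needs two conditions: use must differ by arm, and use must be related to response. The Protocol establishes neither and gives no rates.

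Under the assumptions shown, the consequence ranges from nil or trivial (equal or low use), through a loss of about 10 points of power (84% to 74%), to an inflated risk difference of 0.263 against 0.200. The documents do not support saying that the estimate will be biased, or in which direction. They do support saying that the rule allows it and that the result would then no longer be the declared intention-to-treat effect.

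**What to change.** In the Plan of Statistical Analysis, restrict the covariate to loperamide or fibre use recorded before randomisation and name the source. Candidates are CRF 2, or the Visit 2 concomitant medications log if that entry is timed before allocation. CRF 5 will not serve, because its Visit 2 entry follows the first treatment. If no pre-randomisation record exists, drop the covariate.

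Amend pragmatic consideration 2 under Design to match. Report on-trial use by arm, and label any model that adjusts for it as exploratory.

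The cost is one sentence in the analysis section, the matching edit in Design, and confirmation that pre-randomisation use is captured; the contents of CRF 2 are not shown, so this cannot be assumed. The sample size of 212 does not change.
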